3.2. Sample Size and Power

A sample size of approximately 410 subjects is planned for the study. This sample size is not based on any calculations of power or precision. This sample size will provide a sufficient population size to evaluate the long-term safety of roflumilast foam 0.3% over up to 52 weeks of treatment, and in the combination with other studies provide the development program with sufficient number of subjects to meet ICH exposure goals.

3.3. Study Population

Study population consists of male and female subjects of age 9 years or older with no more than 20% BSA of seborrheic dermatitis.

3.4. Method of Assigning Treatment

Not applicable.

3.5. Treatment Administration

All subjects will be treated with roflumilast foam 0.3% daily (QD).

3.6. Blinding and Unblinding

This is an open-label study and no blinding is planned.

3.7. Schedule of Events

A detailed schedule of events for the study is provided in [Table 1](#).

Table 1: Schedule of Events

Study Procedure	Washout Cohort 2	Day 1 (Cohort 2)	Wk 4 D 29	Wk 12 D 85	Wk 18 D 127	Wk 24 D 169	Wk 30 D 211	Wk 36 D 253	Wk 44 D 309	Wk 52/ ET D 365
Visit	Screening	Final Visit of prior ARQ-154 Study 1 (Cohort 1)	1	2	Phone Visit	3	Phone Visit	4	Phone Visit	5
			+/- 3 days	+/- 5 days	+/- 7 days	+/- 7 days	+/- 7 days	+/- 7 days	+/- 7 days	+/- 7 days
Visit Window	-35 days									
Informed consent/assent	X ^k	X ^k								
Physical examination ^a	X	X ^l				X				X
Medical history	X									
I/E criteria	X	X								
Hematology, Serum Chemistries, and Urine Analysis	X	X ^l	X	X		X		X		X
Vital signs, height, weight ^b	X	X ^l	X	X		X		X		X
IGA ^c , Overall Assessment of Erythema ^c , Overall Assessment of Scaling ^c , WI-NRS, Scalpdex	X	X ^l	X	X		X		X		X
BSA	X	X ^l				X		X		X
C-SSRS, PHQ-8/ PHQ-A/CDI-2 ^d	X	X ^l	X	X		X		X		X
Pregnancy test ^e	X	X ^l	X	X		X		X		X
Local Tolerability Assessment ^f		X ^l	X	X		X		X		X
Pigmentation Assessment ^g	X	X ^l	X	X		X		X		X
Medical Photography ^h		X	X	X		X		X		X
Dispense study medication kit ⁱ		X	X	X		X		X		
IP application at the study site		X								
Dispense/review diary		X	X	X		X		X		X
Weigh study medication		X	X	X		X		X		X
Adverse event assessment ^j	X	X	X	X	X	X	X	X	X	X
Concomitant medications	X	X	X	X	X	X	X	X	X	X

Study Procedure	Washout Cohort 2	Day 1 (Cohort 2)	Wk 4 D 29	Wk 12 D 85	Wk 18 D 127	Wk 24 D 169	Wk 30 D 211	Wk 36 D 253	Wk 44 D 309	Wk 52/ ET D 365
Visit	Screening	Final Visit of prior ARQ-154 Study 1 (Cohort 1)	1	2	Phone Visit	3	Phone Visit	4	Phone Visit	5
			+/- 3 days	+/- 5 days	+/- 7 days	+/- 7 days	+/- 7 days	+/- 7 days	+/- 7 days	+/- 7 days
Visit Window	-35 days									
PK Sampling ^m			X							
Malassezia test ⁿ			X	X		X		X		X

Footnotes from table above:

- ^a Limited physical examination: skin, lungs, and heart only
- ^b Height will be collected at Day 1, Week 24 and Week 52/ET only. Weight will be collected at all study visits. Subject to void prior to weight being taken. Remove any jackets, outerwear and shoes. Remove any objects of significant weight (i.e. cell phones, wallet, key chains). A 5% unintentional weight loss from Baseline should be reported to the medical monitor.
- ^c IGA will be a 5-point scale ranging from completely clear (0) to severe (4). IGA should be completed prior to other physician assessments. Overall assessment of erythema (0-3 scale) and overall assessment of scaling (0-3 scale) will be completed. Total BSA affected by seborrheic dermatitis will be determined at each visit. A body diagram should be used to record areas of seborrheic dermatitis involvement.
- ^d Adolescents and adults will complete the C-SSRS (12 years of age and older). Adults will complete the PHQ-8. Adolescents (ages 12 -17, inclusive) will complete the modified PHQ-A. Parents/caregivers will complete CDI-2 (parent report) for children 9-11 years of age, inclusive.
- ^e A pregnancy test will be administered to all females of child-bearing potential. A serum pregnancy test will be performed at the Screening visit only for Cohort 2. A urine pregnancy test will be performed at Day 1, Weeks 4, 12, 24, 36 and 52. A negative result is required for continued participation in the study, and results must be available prior to dispensing of IP at each visit.
- ^f Local tolerability will be assessed prior to IP application in the clinic for the Investigator assessment of skin (Berger and Bowman skin irritation score) and 10-15 minutes post IP application for the subject's "0-3" burning/stinging assessment at Baseline. Note for Investigator tolerability assessments: **reactions at the site of product application, which may occur post-Baseline, should be differentiated from the preexisting inflammation associated with the subject's seborrheic dermatitis.** At Weeks 4, 12, 24, 36, and 52 will be a recall assessment of burning/stinging experienced post drug application on the previous day of the clinic visit.
- ^g An assessment for hypopigmentation and hyperpigmentation will be performed by the investigator at all clinic visits.
- ^h At selected sites, medical photography will be obtained for target lesions. All efforts will be made to de-identify the subjects. Subjects who are unwilling to participate in the medical photography will be allowed to opt out of this procedure.
- ⁱ Kits will be dispensed based on %BSA affected. See IP Handling Manual for details.
- ^j Any emergent AEs will be followed in the clinic for up to one month at the Investigator's discretion until resolved or otherwise judged as clinically stable.
- ^k For Cohort 1, the consent will be signed after completion of the final visit in prior ARQ-154 study. Cohort 2 will sign consent prior to any study-related procedures at the Screening Visit.
- ^l For Cohort 1, this data will be obtained from the final visit of the prior ARQ-154 Study and used as the Day 1 data for this long-term safety study (ARQ-154-214). If after the prior ARQ-154 study completion, subjects should complete the screening visit procedures. The Baseline values for Safety tabulations will be taken from the day that the subject received their first active IP (across prior ARQ-154 studies and ARQ-154-214). Baseline values for efficacy will be those recorded on Day 1 of the prior ARQ-154 Study. For Cohort 2,

Baseline evaluations will be obtained for all procedures and the Baseline/Screening version of the C-SSRS will be utilized at Screening.

For Cohort 2, Screening labs that are collected within 14 days of Day 1 do not need to be repeated.

^mFor Cohort 2 adolescent subjects PK samples will be collected on Week 4 for adolescent subjects between 12 – 16 years old. Collect PK sample with the safety lab collection. Ensure PK will not be drawn on the areawhere investigational product is applied.

ⁿ At select sites, the Investigator will collect samples for Malassezia testing on Cohort 1 Group 2 subjects at Weeks 4, 12, 24, 36, and 52. Samples will be collected from treated and untreated areas by swabbing the skin surface. Samples should be collected from the same areas as samples collected during the ARQ-154-116 Baseline visit.

4. Statistical Analysis and Reporting

4.1. Introduction

Data processing, tabulation of descriptive statistics, calculation of inferential statistics, and graphical representations will primarily use SAS® (release 9.4 or higher). If the use of other software is warranted, the final statistical methodology report will detail what software was used for what purposes.

Continuous (quantitative) variable summaries will include the number of subjects (n) with non-missing values, mean, standard deviation (SD), median, Q1, Q3, minimum, and maximum.

Categorical (qualitative) variable summaries will include the frequency and percentage of subjects who are in the particular category or each possible value. In general, the denominator for the percentage calculation will be based upon the total number of subjects in the study population for the treatment group unless otherwise specified. The denominator for by-visit displays will be the number of subjects in the relevant study population with non-missing data at each visit.

The minimum and maximum will be reported with the same degree of precision (i.e., the same number of decimal places) as the observed data. Measures of location (mean, median, Q1, and Q3) will be reported to 1 degree of precision more than the observed data and measures of spread (SD) will be reported to 2 degrees of precision more than the observed data, unless otherwise specified or modified upon request of the sponsor.

Percentages will be presented to 1 decimal place, unless otherwise specified.

4.2. Interim Analysis and Data Monitoring

No interim analyses are planned. Once about 400 subjects finish the treatment period in this study, the final analysis will be performed for the full analysis CSR. When all subjects rolled over from study ARQ-154-116 (Cohort 1 Group 2), who enrolled into this ARQ-154-214 study

later than the initial about 400 subjects, finish the treatment in this (ARQ-154-116) study, only listings will be generated for these subjects and these listings will be added as a CSR addendum. No further tables or figures will be generated for these subjects.

5. Analysis Populations

The following analysis populations are planned for this study:

- **All Enrolled (ENRL):** All enrolled population includes subjects who are enrolled into the study (i.e, signed informed consent) and not screen failures.
- **Safety Population (SAF):** The Safety population includes all subjects who are enrolled and received at least 1 confirmed dose of roflumilast foam 0.3% in this extension study.
- **Pruritus Population Primary (PRU4-P):** The PRU4-P population is a subset of the Safety population and includes subjects with WI-NRS pruritus score ≥ 4 at Primary Baseline. This population will be used for the analysis of achievement of a 4-point reduction in WI-NRS pruritus score as compared to Primary Baseline.
- **Pruritus Population Open Label Extension (PRU4-OLE):** The PRU4-OLE population is a subset of the Safety population and includes subjects with WI-NRS pruritus score ≥ 4 at OLE Baseline. This population will be used for the analysis of achievement of a 4-point reduction in WI-NRS pruritus score as compared to OLE Baseline.
- **Pharmacokinetic Population (PK):** The PK population will include all subjects with sufficient plasma concentrations of roflumilast to define a profile, as determined by the pharmacokineticist. This population will be used for analyses of PK parameters.

6. General Issues for Statistical Analysis

For analysis purposes, the tables and figures will be summarized by groups as indicated below.

Cohort 1 Group 1: Subjects rolled over from ARQ-154-203 without gap (Roflumilast Foam 0.3%, Vehicle, Total)

Cohort 2 Group 3: Subjects rolled over from ARQ-154-203 with gap (Roflumilast Foam 0.3%, Vehicle, Total)

Cohort 2 Group 4: De novo subjects

Cohort 2 Total

Overall (includes all Cohorts and groups)

6.1. Statistical Definitions and Algorithms

6.1.1. Baseline

There are three baseline definitions for the analyses:

- Primary baseline is defined as the last observation before the first dose of roflumilast foam 0.3% in either ARQ-154 parent study or this study for subjects administered vehicle previously.
- Open-label baseline (OLE baseline) is defined the last observation before the first dose of roflumilast foam 0.3% in this study. For subjects in Cohort 1 who choose to enroll in this study, study procedures will not be repeated; study sites will carry over the information from the prior ARQ-154 study to the Day 1 visit for this study. For subjects in Cohort 2 Group 4, the definition for Primary and OLE baseline is the same.
- Safety baseline is defined as primary baseline for Cohort 1 Group 1, and OLE baseline for Cohort 2 Group 3 and Group 4.

The following table described the baseline used in the analysis:

Cohort Groups	Prior therapy, medical history	Demog and Efficacy Analysis	Safety Analysis for AE, PHQ8, PHQ-A, Prior and Concomitant medications	Safety Analysis for lab, vital signs and tolerability assessments
Cohort 1 Group 1	OLE baseline	Primary baseline and OLE baseline	OLE baseline	Primary baseline
Cohort 2 Group 3	OLE baseline	Primary baseline and OLE baseline	OLE baseline	OLE baseline
Cohort 2 Group 4	OLE baseline	Primary baseline and OLE baseline	OLE baseline	OLE baseline
Cohort 2 Total	OLE baseline	Primary baseline and OLE baseline	OLE baseline	OLE baseline

Overall	OLE baseline	Primary baseline and OLE baseline	OLE baseline	Safety baseline of roflumilast foam 0.3% in this study for subjects in the safety analysis population. For subjects in Cohort 2 Group 4, the definition for Primary and OLE Baselines is the same
----------------	--------------	-----------------------------------	--------------	---

Baseline values will most commonly be from Day 1.

For subject tolerability assessments, baseline is derived as the last non-missing measurement taken on the day of first application of study drug.

6.1.2. Multiple Comparisons

No adjustments for multiple comparisons will be made for this study. No inferential statistical analyses are planned for this study.

6.1.3. Handling of Dropouts or Missing Data

Other than what is mentioned in 6.1.8, no data will be imputed in the analyses for this study.

6.1.4. Analysis Visit Windows

Visits will be analyzed as scheduled. Unscheduled, early termination visits, and/or repeated measurements will only be included if a scheduled measurement is not available and the early termination or unscheduled/repeated measurement falls within the analysis visit windows as described in [Table 2](#) and [Table 3](#). The windows follow the Schedule of Events in [Table 1](#). For subjects in Cohort 2 Group 3, the gap between completion of parent study and starting of the study ARQ-154-214 should not be counted in the analysis visit window. The windowing will be applied using the days on study as shown in the [Table 2](#). Unscheduled/repeated measurements will be listed.

Table 2: Analysis Visit Windows (Primary Baseline for Cohort 1 Group 1 & Cohort 2 Group 3)

		Primary Baseline for Group 1 - Roflumilast & Group 3 - Roflumilast	
Scheduled Visit	Target Days on Study	Window (Days)	

ARQ-154-203 Week 2	14	2 to 22
ARQ-154-203 Week 4	28	23 to 42
ARQ-154-203 Week 8	56	43 to 61
Week 4 OLE	85	71 to 113
Week 12 OLE	141	114 to 183
Week 24 OLE	225	184 to 267
Week 36 OLE	309	268 to 365
Week 52 OLE	421	≥ 366

Table 3: Analysis Visit Windows

Primary Baseline for Cohort 1 Group 1 - Vehicle & Cohort 2 Group 3 - Vehicle Cohort 2 Group 4 + OLE Baseline for Cohort 1 Group 1 - Roflumilast & Cohort 2 Group 3 – Roflumilast		
Scheduled Visit	Target Study Day	Window (Days)
ARQ-154-203 Week 2	n.a.	n.a.
ARQ-154-203 Week 4	n.a.	n.a.
ARQ-154-203 Week 8	n.a.	n.a.
Week 4 OLE	29	15 to 57
Week 12 OLE	85	58 to 127
Week 24 OLE	169	128 to 211
Week 36 OLE	253	212 to 309
Week 52 OLE	365	≥ 310

n.a. = not applicable

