6.4. Early Termination Visit

If a subject is withdrawn from the study, a termination visit will be scheduled. This visit should include the procedures and assessments that would be performed at the Week 52 visit. It will be noted in the database which subjects have completed the study and which were early terminations.

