8.2. Secondary Efficacy Analysis

8.2.1. Investigator Global Assessment (IGA)

The IGA is an ordinal scale with five severity grades which is reported only in integers.

[Table 4](#) illustrates the description of each severity grade.

Table 4: IGA

Score	Description
0	Completely clear: No erythema, no scaling (hypo-hyperpigmentation can be present)
1	Almost clear: Residual slight erythema and/or trace amounts of scaling
2	Mild: Pink to red color and/or slight scaling
3	Moderate: Distinct redness and/or clearly visible scaling
4	Severe: Severe erythema (intense, fiery red) and/or severe scaling (coarse, thick scales with flaking onto clothes or skin)

IGA grade

IGA grade and change from baseline will be summarized using descriptive statistics at each visit by groups and overall.

The number and percentage of subjects in each IGA grade category will be summarized by cohort, group, and overall.

The number and percentage of subjects who achieve IGA 0 or 1 will be tabulated at each scheduled visit by groups and overall. In addition, the achievement of IGA of 0, the achievement of IGA success (i.e., IGA of 0 or 1 plus a 2-grade improvement from Baseline) also will be tabulated. Furthermore, 95% CIs for proportion of subjects who meet the criteria will be provided along with proportions. IGA success from OLE baseline should exclude subjects who already achieved IGA of 0 or 1 at OLE baseline.

IGA success, IGA of 0 or 1, IGA of 0 at any time post baseline including the assessments at the unscheduled visit will be summarized by groups and overall, along with 95% CIs for proportion of people who meet the criteria.

These analyses are repeated for both primary and OLE baselines. The subjects who achieved IGA of 0 or 1 at baseline will be excluded from the analysis of IGA success from baseline.

Subgroup analyses will be performed for both primary and OLE baseline for the subgroups mentioned in Section [6.1.6](#).

Duration of IGA success, Duration of IGA of 0 or 1, and Duration of IGA of 0

This analysis will be performed using IGA grade assessed in the open-label study.

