9.3. Clinical Laboratory Evaluations

Laboratory test results will be summarized descriptively by groups and study visit as both observed values, changes, and percent changes from baseline values for continuous hematology, chemistry, and urinalysis results. Categorical urinalysis results will be summarized using frequencies by groups and study visit.

The number of subjects with clinical laboratory values below, within, or above the normal range by study visit and in relation to baseline will be tabulated for each clinical laboratory analyte (shift table).

Primary baseline will be used for Cohort 1 Group 1 and OLE baseline for Cohort 2. Overall group will be summarized using Safety baseline.

Abnormal laboratory values will be presented in the listings.

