9.4. Vital Signs

Descriptive summaries of observed values, changes, and percent changes from baseline will be calculated for systolic blood pressure, diastolic blood pressure, heart rate, height, weight, body mass index, and oral body temperature by group and study visit.

Categorical percent changes in weight (i.e., shifts from baseline) by group will be summarized by the number of subjects who gain or lose $\geq 5\%$ of their baseline body weight during the course of the study, as well as subjects who gain or lose $\geq 10\%$ of their baseline body weight over the course of the study by groups and study visit.

BMI is derived as specified in Section [6.1.7](#). Shift tables for subjects who shift from their baseline BMI category (underweight, normal, overweight, obese) to a different BMI category throughout the course of the study will be provided by groups and study visit.

Shift tables for weight and BMI will also be summarized by intentional and unintentional weight loss (defined from question on vital sign eCRF). Vital signs summaries will use primary baseline for Cohort 1 Group 1 and OLE baseline for Cohort 2. Overall group will be summarized using Safety baseline.

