9.5. PHQ-8

PHQ-8 will be completed by adult subjects and modified PHQ-A will be completed by adolescent subjects of age 12-17 years inclusive. Data for PHQ-8 and Modified PHQ-A will be classified using each subject's total score at a time point into a category based on the following scoring system:

- None – Minimal depression (0 to 4)
- Mild depression (5 to 9)
- Moderate depression (10 to 14)
- Moderately severe depression (15 to 19)
- Severe depression (20 to 24)

Shift tables showing the category of severity at each study visit will be presented by group. As PHQ-A is not assessed in ARQ-154-203 study, only OLE baseline will be used for this summary.

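### Early-termination values taken after the scheduled visit in the same window, or before Day 15, stay out of the by-visit lab, PHQ and tolerability tables, and no last-value or worst-value row recovers them

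*SAP*

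**What the plan says.** SAP 6.1.4 sets one rule for all visit-based data: "Unscheduled, early termination visits, and/or repeated measurements will only be included if a scheduled measurement is not available". There is a second condition: the value counts only if the "early termination or unscheduled/repeated measurement falls within the analysis visit windows" of Table 2 or Table 3. The section makes no exception for safety data. It adds that "Unscheduled/repeated measurements will be listed", a sentence that does not name early-termination values.

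Protocol 6.4 describes the exit visit for a withdrawn subject: "This visit should include the procedures and assessments that would be performed at the Week 52 visit". By the schedule of assessments, that means labs, weight, PHQ, C-SSRS and tolerability.

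The safety sections of the SAP work visit by visit:
- **Labs (9.3):** "Laboratory test results will be summarized descriptively by groups and study visit", with the shift table also by visit.
- **PHQ (9.5):** "Shift tables showing the category of severity at each study visit will be presented by group".
- **Tolerability (9.2):** counts and means of scores. Protocol 7.2.2 says these are by visit.
- **Weight (9.4):** one sentence counts subjects with 5% and 10% changes both over the study as a whole and by visit.

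For comparison, SAP 8.2.1 provides for IGA results "at any time post baseline including the assessments at the unscheduled visit will be summarized by groups and overall".

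**The concern.** Long-term safety is the study's only objective. A subject who withdraws has a complete set of exit measurements, yet in Table 3 the windows for Weeks 4 to 36 run well past the target day. The Week 24 window, for example, covers Days 128 to 211 around a target of Day 169. A subject seen on Day 169 who leaves on Day 185 has exit labs, PHQ and tolerability scores that enter no by-visit row. No other row in SAP 9.2, 9.3 or 9.5 takes them up.

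These values may carry information. Protocol 5.4.3 and 6.8 make unintentional weight loss, a high PHQ score and a confirmed related Grade 3 lab abnormality grounds for stopping, or for considering stopping, the product. If subjects leave for such reasons, the exit value may be abnormal, and tables without it can understate abnormality.

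**Working it through.** The plan states no share of exit visits lost, no withdrawal rate and no withdrawal timing, so there is no figure to reproduce. The share below is derived from the windows.

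**Inputs.** Target days and windows are from SAP Table 3. Protocol 1.3 gives visit tolerances of ±3, ±5 and ±7 days.

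**Step 1: count days on which an exit visit is kept or left out.** Assume scheduled visits fall on target and earlier visits were attended. Exit days run from 2 to 364.

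| Window | Target | Days before target (kept) | Days after target (left out) |
|---|---|---|---|
| none (2–14) | – | – | 13 |
| Week 4 (15–57) | 29 | 14 | 28 |
| Week 12 (58–127) | 85 | 27 | 42 |
| Week 24 (128–211) | 169 | 41 | 42 |
| Week 36 (212–309) | 253 | 41 | 56 |
| Week 52 (310 on) | 365 | 55 | 0 |

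Kept: 14 + 27 + 41 + 41 + 55 = 178. Left out after a scheduled value: 28 + 42 + 42 + 56 = 168. Left out with no window: 13.

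Share left out = (168 + 13) / (178 + 181) = 181/359 = 50.4%. If the four target days 29, 85, 169 and 253 are counted as kept, it is 181/363 = 49.9%.

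**Step 2: check Table 2.** This table serves the roflumilast rollovers from primary baseline. Its open-label targets and window bounds are those of Table 3 plus 56 days (for example 15 + 56 = 71 and 57 + 56 = 113), so the 168 days are unchanged. Open-label Days 2 to 14 become Days 58 to 70. Days 58 to 61 fall in the parent-study Week 8 window, which already holds a scheduled value, and Days 62 to 70 fall in no window. The total left out is again 181.

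**Step 3: vary the assumptions.**

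| Assumption about exit visits | Share left out |
|---|---|
| Uniform timing, visits varied within tolerance (simulated) | 50.3% |
| Constant hazard, 10% to 70% cumulative withdrawal (simulated) | 51% to 53% |
| Mid-loaded, Beta(2,2) (simulated) | 53% |
| Front-loaded, Beta(1,2) to Beta(1,5) (simulated) | 56% to 59% |
| Back-loaded, Beta(2,1) to Beta(3,1) (simulated) | 45% to 41% |
| 10%, 20%, 30% of earlier visits missed: (13 + 168 × (1 − m)) / 363 | 45%, 41%, 36% |
| Half of withdrawals made at a scheduled visit: 0.5 × 50% | 25% |

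**Step 4: illustrate the number of subjects.** Assume that 10% to 30% of about 400 subjects withdraw, that is 40 to 120. At 50%, 20 to 60 exit assessments are left out. Over the range 25% to 59% the limits are 40 × 0.25 = 10 and 120 × 0.59 ≈ 71. These are upper figures, because deaths and losses to follow-up produce no exit visit.

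**The case against.** Several points weigh on the other side.

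- **The rule is blind to the value.** A reader might infer that it selectively removes abnormal results and so biases the tables towards normal. The documents do not show this. Labs, weight and PHQ are collected at scheduled clinic visits, so the abnormal value that prompts withdrawal will often be the scheduled one, which stays in the table. After an abnormal scheduled lab, the rule also stops a later normal repeat from replacing it. This stands: understatement is possible, not demonstrated.
- **Safety does have any-time or worst-case summaries.** A reader might set the IGA row against the safety tables and conclude that the plan captures the best efficacy value but never the worst safety value. That goes too far. TEAEs are tabulated by maximum severity (SAP 9.1), and C-SSRS ideation and behaviour are defined over the whole treatment period (SAP 6.1.7). The weight sentence can be read as an any-time count. The IGA row also has a design reason, since unscheduled visits confirm clearance (Protocol 5.6.3 and 6.5). The gap is confined to labs, PHQ and tolerability, with weight unclear.
- **The signal is caught elsewhere.** TEAEs and SAEs, the primary endpoints, do not depend on visit windows. TEAEs leading to withdrawal are tabulated, and unscheduled values and abnormal labs are listed. All true, but a listing does not change a shift-table count.
- **Unscheduled visits add little.** Protocol 6.5 does not list PHQ or weight among the items collected there. This stands; the point rests mainly on early-termination visits.

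**Conclusion.** The point holds in a limited form. For labs, PHQ and tolerability, early-termination values that follow a scheduled value in the same window, or come before Day 15 on the Table 3 scale, do not reach the by-visit tables, and no last or worst post-baseline summary is specified. What is lost is the subject's later value; the scheduled value in the window remains. Exit visits on Days 310 to 364 are kept as Week 52.

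About half of exit visits are affected if timing is uniform and earlier visits were attended. That share is an assumption, not a property of the plan. The working gives 41% to 59% over smooth timing patterns, 36% to 45% if 10% to 30% of earlier visits were missed, and 25% if half of withdrawals occur at a scheduled visit. No count of subjects can be fixed without a withdrawal rate. The tables can understate abnormality; whether they would, and by how much, cannot be settled from the documents.

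**What to change.** - **SAP 9.2, 9.3 and 9.5:** keep the by-visit rows. Add a 'last post-baseline' row and a 'worst post-baseline' row (lab shift, highest PHQ category, highest tolerability score), using all scheduled, unscheduled and early-termination data.
- **SAP 9.4:** state that the 5% and 10% weight-change counts include an any-time post-baseline row from the same data. This settles the ambiguous sentence.
- **SAP 6.1.4:** state that the window restriction does not apply to these rows.

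The cost is SAP wording and a few extra table rows, with no new data or procedures. Abnormality counts may look slightly less favourable.
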